1.1 Relevance & Innovation

Women in Ghana suffer from one of the highest perinatal mortality rates in the world. Every day in Ghana, 47 babies are stillborn (1) and 232 babies are born with LBW (20) – many of whom will die in infancy or suffer lifelong consequences. As such, Ghana urgently requires inexpensive interventions to reduce perinatal morbidity and mortality – assisting pregnant Ghanaian women to avoid sleeping on their back might be one such intervention.

A maternal positional therapy device, called “PrenaBelt”, has been developed by members of our team ([name], [name]) to modify maternal sleep position and mitigate this risk factor. The Ghana PrenaBelt Trial (Principal Investigator: [name]; Ethics: NMIMR-IRB#069/14-15, IWK-REB#1019318; Regulation: FDA/CT/152, NCT02379728) is a sham-controlled, double-blind, randomized trial in N=200 healthy, third-trimester pregnant women at the Korle Bu Teaching Hospital Obstetrics and Gynaecology Department. The purpose of the Ghana PrenaBelt Trial is to determine the effect of

PrenaBelt use during sleep throughout the third trimester on birth weight. Recruitment for the Ghana PrenaBelt Trial was 100% complete on 02MAR2016 and data collection was completed on 25JUN2016.

1.2 Rationale

At the half-way point in the Ghana PrenaBelt Trial (“GPT”) (n=41 births in each group), no difference in birth weight was found between the two groups (PrenaBelt versus sham-PrenaBelt) on a two-sample t-test (p=0.51). Conclusions were the same using a non-parametric method (Wilcoxon rank sum test). Note that hypothesis for the GPT is that the birth weights will be higher in the PrenaBelt group than in the sham-PrenaBelt group.

The GPT was originally proposed as a randomized controlled trial with a treatment (PrenaBelt) group and a control (no PrenaBelt) group; however, the Noguchi-IRB strongly recommended that the study be sham-controlled and double blinded. Our team elected to follow the IRB’s recommendation.

In the GPT, participants are educated on the rationale for the study as part of the informed consent process, i.e., back sleep in late pregnancy has been recently implicated as a possibly modifiable risk factor for stillbirth and low birth weight. Participants are subsequently randomized to receive treatment with a PrenaBelt or a sham-PrenaBelt and are blinded to their treatment allocation.

Given the results of the interim analysis, it is questioned if the back-sleep education during the consent process could be having an effect on the sleep behaviour of the participants independently of their treatment allocation. The GPT Team reports that the education could be having an effect, for example, some participants in the sham-PrenaBelt group have reported that they stopped using their assigned device because they had since trained themselves to sleep exclusively on their left side using alternative means.

Many campaigns have had unprecedented impact on public health by education alone, for example, the “back-to-sleep” campaign to prevent sudden infant death syndrome. Therefore, since both the PrenaBelt (treatment) and sham-PrenaBelt (sham-control) groups have received back-sleep education, our team contends that an investigation of a third group without back-sleep education, a true control group, is warranted for comparison.

2 Research Question

What is the mean birth weight and standard deviation of babies born to a cohort of women who:

- Meet the same inclusion/exclusion criteria as the cohort in the Ghana PrenaBelt Trial,
- Have not received education that back sleep during late pregnancy is a possible modifiable risk factor for low birth weight and stillbirth,
- Did not participate in the Ghana PrenaBelt Trial, and
- Gave birth to their babies in a similar time period (year 2016) as the Ghana PrenaBelt Trial?

3 Aims

To establish a reference birth weight (mean and standard deviation) of babies born to a cohort of women comparable to the cohort in the Ghana PrenaBelt Trial but who have not received back-sleep education, did not participate in the Ghana PrenaBelt Trial, and whose babies were born in a similar time period and weighed on the same newborn scales. This reference birth weight will serve as a control for the Ghana PrenaBelt Trial.

3.1 Specific Objectives

[figure not shown]
1. Conduct a review of hospital records to confirm the control group participants meet the inclusion/exclusion criteria of the Ghana PrenaBelt Trial and record the:
 - a. Birth weight
 - b. Date of delivery
 - c. Mode of delivery
 - d. Gestational age at delivery
2. Administer a questionnaire to collect demographic, obstetric, and sleep habit data for characterization of the control group and comparison of the control group to the groups (treatment, sham-control) in the Ghana PrenaBelt Trial.

4 Literature Review

In 2009, the World Health Organization reported the global prevalence of stillbirth (SB)

to be 2.6 million (uncertainty range: 2.1-3.8 million), of which 98% occur in low- and middle-income countries (1) – see Figure 1.

[figure not shown]
In addition to the global burden of SB, the global incidence of LBW infants remains a significant public health challenge. Each year, there are over 20 million infants born with LBW, of which 96% occur in low- and middle-income countries with the highest concentrations in Asia and Africa (2) – see Figure 1. Efforts to reduce the incidence of LBW have not been successful in these regions, and thus the incidence has remained largely unchanged (2).

In the Auckland Stillbirth Study (17), the population attributable risk (PAR) for non-left sleep position to SB was found to be 37%, which is greater than the PARs of the three most important modifiable risk factors for SB (obesity, advanced maternal age, and smoking) combined (3). In an African population (18), members of our team ([name], [name])

found that back sleep during pregnancy was an independent predictor of LBW (OR, 5.0; 95% CI, 1.2–20.2; P=0.025) and SB (OR, 8.0; 95% CI, 1.5–43.2; P=0.016), when controlling for covariates maternal age, gestational age, parity, and the presence of pre-eclampsia. Notably, LBW was found to mediate the relationship between back sleep and SB (18). In the Sydney Stillbirth Study (16), the back sleep position was associated with SB (adjusted OR, 6.26; 95% CI, 1.2–34) and the PAR for reported back sleep was 9.88% (95% CI, 5.67-14.1%). Currently, there is much interest (21) and follow up research occurring worldwide (22).

One proposed model for maternal back sleep playing a causative role in low birth weight and stillbirth is that back sleep is a “fetal stressor” via compression of the abdominal aorta and inferior vena cava (‘aortocaval compression’) when lying on the back, and, when combined with “maternal factors” and “placental or fetal vulnerability”, may result in negative sequelae. This model is known as the triple-risk model for late unexplained stillbirth (23) – see Figure 2. Our team proposes that by mitigating the “fetal stressor”, we may protect the fetus from LBW or SB.

Some pregnant women sleep with many pillows supporting their body, including a pillow behind their back to avoid the supine position. Indeed, we expect that some pregnant women in Ghana may increase the amount of time that they spend sleeping on their left side as their pregnancy progresses perhaps due to hearing or reading a “sleep on the left in pregnancy” or “SOS” (Sleep-On-Side) message, for example, hearing about the Ghana PrenaBelt Trial or browsing other resources (24).

Our colleague and team member from Australia ([name]), has recently published data (25) relevant to the issue under consideration in this research protocol:

- Moderate correlation between diary-reported and video-determined indicators of sleep position indicates that third-trimester pregnant women are reliable when self-reporting their sleep position.
 - Comment: This lends credence to anecdotal reports of participants in the sham-control group in the GPT who report that they have trained themselves to sleep on their left side.
- Instructing third-trimester women to sleep on their left side can increase the percentage of left-sided sleep to approximately 60% of the night; however, this can be highly variable (ranging from 11% to 98%) and may come at a cost of a slightly reduced sleep duration for women who do not normally adopt the left position, perhaps due to women feeling they need to make a conscious effort to maintain the left sleep position.
 - Comment: This lends credence to our hypothesis that back-sleep education may be having an independent effect on sleep behavior in the GPT regardless of treatment assignment.
- When third-trimester pregnant women are instructed to sleep on their left, the percentage of time spent sleeping on the left side is relatively consistent within individuals across multiple nights, with an average difference of only 15% between nights (maximum 40%).
 - Comment: If participants in the sham-control group in the GPT have truly trained themselves to sleep on their left side, this indicates that many will be able to consistently maintain the left side position throughout the remainder of their pregnancy without the assistance of a device.

5 Methodology

5.1 Study Design

This study will be of a cross-sectional design.

5.2 Study Site

This study will be conducted at the Korle Bu Teaching Hospital within the Obstetrics and Gynaecology Department (labor wards, Biostatistics Department, [name] office). The existing KBTH infrastructure (Detecto digital newborn scales installed by GIRHL in partnership with KBTH) and existing Ghana PrenaBelt Trial instrumentation (laptop, tablet, Surflin, printer, scanner/copier, filing cabinet, stationary – all property of GIRHL) will be used for this study.

5.4 Sample Size Determination

A sample size of one-hundred sixty-two (N=162) participants is selected for the KBTH-GIRHL Healthy Birth Weight Study. N=162 is the minimum combined group size for the Ghana PrenaBelt Trial: n=81 treatments plus n=81 sham-controls. The Ghana PrenaBelt Trial sample size was statistically justified (using power of 0.8 and type I error probability of 0.05 and accounting for 20% lost to follow up) based on a previous study in a Ghanaian population by members of our team ([name], [name]) (18) and using the PS Power and Sample Size Program (Version 3.0).

In order to avoid variance bias in comparison of the non-educated (KBTH-GIRHL Healthy Birth Weight Study) group to the back-sleep educated group (Ghana PrenaBelt Trial), the group sizes should be the same; therefore, one-hundred sixty-two (N=162) participants will be included in this study to match the 162 (minimum) participants in the Ghana PrenaBelt Trial. Since this is a cross-sectional study to recruit a control group only, no participants in this study will be lost to follow up; therefore, 162 participants are required in this study.

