Cover Page

Statistical Analysis Plan

Official Title: Korle Bu Teaching Hospital - Global Innovations for Reproductive Health & Life
Healthy Birth Weight Study: A Cross-Section

NTC03062228

Document Date: 20JUL2016

Statistical Analysis Plan

1. Designation of Personnel

All analyses described will be performed by the Project Lead and Co-Investigator, [name], under the supervision of the consulting statistician, [name]. The analyses described will be performed using the R statistical software package (version 3.2.0., “Full of Ingredients”).

2. Outcome measurements

Primary Outcomes:

- Birth weight
- Customized birth weight centile

Secondary outcomes:

- Gestational Age at Delivery
- Small for Gestational Age
- Low Birth Weight
- Sex of Newborn
- Preterm Delivery
- Mode of Delivery

3. Sample size calculation

A sample size of one-hundred sixty-two (N=162) participants is selected for the KBTH-GIRHL Healthy Birth Weight Study. N=162 is the minimum combined group size for the Ghana PrenaBelt Trial (NTC02379728): n=81 treatments plus n=81 sham-controls. The Ghana PrenaBelt Trial sample size was statistically justified (using power of 0.8 and type I error probability of 0.05 and accounting for 20% lost to follow up) based on a previous study in a Ghanaian population by members of our team ([name], [name]) and using the PS Power and Sample Size Program (Version 3.0).

In order to avoid variance bias in comparison of the non-educated (KBTH-GIRHL Healthy Birth Weight Study) group to the back-sleep educated group (Ghana PrenaBelt Trial), the group sizes should be the same; therefore, one-hundred sixty-two (N=162) participants will be included in this study to match the 162 (minimum) participants in the Ghana PrenaBelt Trial. Since this is a cross-sectional study to recruit a control group only, no participants in this study will be lost to follow up; therefore, 162 participants are required in this study.

4. Treatment randomization

Not applicable. This is a cross-sectional study; therefore, no randomization is performed.

5. Interim safety analysis

Not applicable.

6. Analyses at study termination

Descriptive statistics will be employed for collected demographic, obstetric, and sleep habits information from the Data Collection Questionnaire and outcome measures from the Delivery Outcome Form.

Interpretation of the results from this study will be conducted in conjunction with results from the Ghana PrenaBelt Trial as follows:

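### The reason given for N=162, equal group sizes to avoid variance bias, is not valid, and the plan does not say which GPT births enter the comparison (minor)

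*Protocol*

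**What the plan says.** Protocol 5.4 fixes the size of the new control group: "A sample size of one-hundred sixty-two (N=162) participants is selected for the KBTH-GIRHL Healthy Birth Weight Study". The figure is taken from the GPT: "N=162 is the minimum combined group size for the Ghana PrenaBelt Trial: n=81 treatments plus n=81 sham-controls". The GPT size is in turn said to rest on a calculation "using power of 0.8 and type I error probability of 0.05 and accounting for 20% lost to follow up", without an effect size or a standard deviation.

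The reason for carrying that number over is equality of the two groups. SAP section 3 opens the argument with "In order to avoid variance bias in comparison of the non-educated", and Protocol 5.4 concludes that "the group sizes should be the same; therefore, one-hundred sixty-two (N=162) participants will be included in this study to match the 162 (minimum) participants". The two documents share this text.

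Protocol 1.1 describes the GPT as a "randomized trial in N=200 healthy, third-trimester pregnant women" and reports its status: "Recruitment for the Ghana PrenaBelt Trial was 100% complete on 02MAR2016 and data collection was completed on 25JUN2016". The SAP is dated 20JUL2016.

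For the educated v non-educated comparison, Protocol section 7 and SAP section 6 name the paired t-test for normal continuous outcomes and the Wilcoxon signed rank test otherwise. The same sections say that all analyses follow intention to treat. Neither document gives the number of GPT births available, a rule for forming pairs, or a rule for choosing among GPT births.

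**The concern.** There are three linked difficulties.

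- **The reason is not a statistical one.** With independent groups, unequal sizes bias neither the difference in means nor its variance when each group's variance is estimated separately. The nearest real problem arises when a pooled-variance t-test is used, the sizes differ and the SDs also differ. Welch's test deals with that without constraining the sizes.
- **The number matched is a planning figure.** The Protocol itself records that GPT data collection had ended, so the actual count of births could have been known when both documents were finalised. Equality with 162 would hold only if the GPT yielded exactly 162 births, or if some were set aside.
- **The analysis set is left open.** A statement that sizes should be equal, next to tests that need equal numbers, sits badly with an intention-to-treat statement that points to using every randomised woman. If more than 162 GPT births exist, the plan does not settle which enter the primary comparison. Those outcomes were already collected, and Protocol 1.2 reports an interim look at birth weight.

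At stake are a little precision and an avoidable analytic choice made after the data exist. Without the variance-bias argument, 162 also has no stated justification for this contrast, because the power statement belongs to PrenaBelt v sham.

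**Working it through.** **Inputs.** Controls: 162 (Protocol 5.4). GPT minimum: 81 + 81 (Protocol 5.4). GPT enrolment: 200, recruitment complete (Protocol 1.1). Planned GPT loss: 20% (Protocol 5.4). The documents give no birth-weight SD, so results are in SD units, assuming equal SDs unless stated.

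**1. The plan's own figure.** 81 + 81 = 162, which reproduces. Inflating for 20% loss gives 162/0.8 = 202.5 (203), or 162 × 1.2 = 194.4 (195). Either is close to 200, so 162 looks like the target after loss and 200 the gross enrolment. The 81 per arm cannot be rebuilt without an effect size and SD.

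**2. GPT births beyond 162.**
- No loss: 200 − 162 = 38, which is 38/200 = 19%.
- 20% loss: 200 × 0.8 = 160 births, so none.

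A paired analysis uses at most the smaller of 162 and the number of GPT births, so the unused GPT births range from 0 to 38.

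**3. Precision.** SE = SD × √(1/n₁ + 1/n₂). Detectable difference at 80% power, two-sided 5%: (1.960 + 0.842) × SE.

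| Controls v GPT | SE (SD units) | Detectable difference (SD units) |
|---|---|---|
| 162 v 162 | 0.1111 | 0.311 |
| 162 v 180 | 0.1083 | 0.303 |
| 162 v 200 | 0.1057 | 0.296 |

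Ratio of the extremes: 0.1057/0.1111 = 0.951, so the SE is 4.9% smaller; 0.951² = 0.905, so the variance is 9.5% smaller. Power for a 0.311 SD difference rises from 80.0% to 83.8%. If the SD were 400 to 500 g (an assumption), the 95% half-width, 1.96 × SE, would be 87 to 109 g at 162 v 162 and 83 to 104 g at 162 v 200.

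**4. Do unequal sizes cause bias?** In 20,000 simulated comparisons at 162 v 200 for each of three GPT/control SD ratios (0.8, 1 and 1.25), the mean difference was off by at most 0.002 SD. Welch's type I error was 4.7% to 4.8%.

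**5. The pooled t-test, both directions.** With n₁ = 162 and n₂ = 200, the true variance of the difference is V = σ₁²/n₁ + σ₂²/n₂. The pooled test estimates P = [((n₁−1)σ₁² + (n₂−1)σ₂²)/(n₁+n₂−2)] × (1/n₁ + 1/n₂). Its large-sample size is 2 × [1 − Φ(1.96 × √(P/V))].

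| SD pattern | √(P/V) | True size |
|---|---|---|
| GPT SD 1.2 times control | 1.019 | 4.6% |
| GPT SD 1.4 times control | 1.035 | 4.3% |
| Control SD 1.2 times GPT | 0.981 | 5.4% |
| Control SD 1.4 times GPT | 0.966 | 5.8% |

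The SD ratios are illustrative. At equal sizes the same formula gives 5.0% whatever the ratio.

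**The case against.** The strongest reply is that the equal-size sentence is a recruitment target and does not define an analysis set. It fixes how many controls to enrol, calls the GPT figure a minimum, and sits in a plan that specifies intention to treat. Nothing caps, samples or discards GPT births. A reader might infer that following the plan means ignoring up to 38 GPT births. The documents do not support that: no passage orders it, and at the planned 20% loss only 160 births would exist. This part of the reply stands.

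It is also fair that 162 is a coherent number to match. It agrees with 200 enrolled less about 20%, and Protocol 1.2 puts the half-way point at 41 births per group, about half of 81. Controls are enrolled after delivery, so matching them to the target after loss makes sense. It would go too far to call 162 simply the wrong number. The weakness is that a planned figure is used where the actual one could have been known.

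Equal sizes do give some protection: they hold a pooled t-test at its nominal size when the SDs differ, including when the smaller control group has the larger SD. But the effect here is under one percentage point, the plan names no pooled test, and Welch makes the protection unnecessary.

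Finally, using paired tests on unmatched groups is a defect in its own right, and correcting it removes any need for equal counts. That is true. It does not rescue the variance-bias reason or supply the missing statement of which GPT births are used.

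**Conclusion.** The point holds as a minor one. The variance-bias reason is not valid, and it is the only support offered for 162 in the educated v non-educated comparison. The GPT had enrolled 200 and finished collecting data before the SAP date, yet the plan states neither how many GPT births are available nor that all will be used. The equal-size statement together with the paired t-test and signed rank test would allow at most 162 arbitrary pairs and leave 0 to 38 GPT births out. The upper end needs no loss at all, and the documents do not give the actual count.

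The consequence for precision is small, at most 4.9% in the standard error, assuming equal SDs. The plan does not introduce bias by choosing 162. The case for a change rests on removing a wrong premise and closing an undefined choice, more than on the precision gained.

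**What to change.** In Protocol 5.4 and SAP section 3:

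- Delete the equal-size, variance-bias reason.
- Describe 162 by the precision it gives: at 80% power and two-sided 5%, a detectable difference of about 0.31 SD with 162 GPT births and 0.30 SD with 200.
- Give the actual number of GPT births with a recorded weight.

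In Protocol section 7 and SAP section 6:

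- State that every GPT woman with a recorded birth weight is compared with all enrolled controls, whatever the ratio.
- Replace the paired t-test with an independent-samples Welch t interval for the difference in means. If a rank-based test is kept, use the rank sum test in place of the signed rank test. Protocol 1.2 already reports a two-sample t-test and a rank sum test for the GPT interim comparison.

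The cost is wording in two documents. No further recruitment or data collection is needed, since GPT data collection is complete.

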5.5 Procedures

1. Each participant will be screened, consented, and enrolled per Section 9.4 – Process for Seeking Consent.
2. Each enrolled participant will be assigned a six-digit alpha-numeric code by the study personnel. As each new participant is enrolled, the study personnel will construct the key to this code, which links the code to the participant's KBTH hospital record. This key will be kept strictly confidential by the study personnel - see Section 9.3 Minimization of Potential Harms for data security and privacy/confidentiality protection measures. All study data will be collected only in association with this code, thus automatically de-identifying the data.
3. The study personnel will complete the Data Collection Questionnaire with each participant. Since the questionnaire will be administered on the wards, it is possible that the participant's responses may be overheard by others other than the study personnel conducting the questionnaire; therefore, the participant will be informed

that she may refuse any question that she feels uncomfortable answering. It is expected that the questionnaire will take ten to fifteen minutes to complete.

4. After the study personnel completes the questionnaire with the participant, the study personnel will review the participant's KBTH hospital record and complete the participant's Delivery Outcomes Form.
5. For each participant, the study personnel will upload the Data Collection Questionnaire and Delivery Outcomes Form data (both documents include de-identified data only) to the research team's secure Microsoft OneDrive cloud for data extraction in preparation for the data analysis by the research team.

6 Data Handling

All study personnel involved in the conduct of this study at the study site ([name], [name]) and data handling have received Good Documentation Practice (GDP) training as part of the Ghana PrenaBelt Trial within the past two years. Reference Section 10 and Section 34 in the Ghana PrenaBelt Trial Site Study Master Record (FDA regulatory file) in [name] office. Also reference GIRHL-SOP.005 – Guidelines for Completing Forms in the Ghana PrenaBelt Trial SOP/SSP Binder in [name] office. In addition, [name] has completed Good Clinical Practice training with the Ghana Food and Drugs Authority in the past two years.

All study personnel involved in off-site data handling and data quality monitoring ([name], [name]) have completed Tri-Council Policy Statement (TCPS-2) training within the past two years. In addition, [name] has completed Good Clinical Practice (GCP) training for investigators from the Collaborative Institutional Training Initiative (CITI) Program within the past two years.

See Section 9.3 Minimization of Potential Harms for measures in place to ensure data security and protect participant privacy and confidentiality.

7 Statistical Analysis

Descriptive statistics (mean, median, standard deviation, maximum, minimum) will be employed for collected demographic, obstetric, and sleep habits information from the Data

Collection Questionnaire and key measurements (e.g., birth weight, gestational age at delivery) from the Delivery Outcome Form.

Interpretation of the results from this study will be conducted in conjunction with results from the Ghana PrenaBelt Trial (GPT) as follows:

- Comparison of groups (back-sleep education, no back-sleep education):
 - For continuous variables, the assumption of normality will be assessed using Q-Q plots and the Anderson-Darling test.
 - If normal, paired t-test will be used for evaluating differences.
 - If non-normal, Wilcoxon signed rank test will be used for evaluating differences.
 - For dichotomous and categorical data, we will evaluate for differences using Chi-squared, Fisher's exact test, or McNemar's test for repeated measurements.
- Note that all analyses will be conducted via the intention-to-treat approach in order to provide unbiased comparisons among treatment groups.

Central quantitative data will be sorted and stored in Microsoft Excel files. Quantitative data analysis will be performed in the R statistical software. We will report the number of participants with missing data.

Any deviations from the original statistical plan will be done under the supervision of our consultant statistician on the GPT ([name], M.Sc. Statistics, MD Candidate 2018) and described in full and justified in the final report, as appropriate.

8 Dissemination of Results

Since the results of this study will be interpreted and presented in conjunction with the results of the Ghana PrenaBelt Trial (GPT), we will follow the dissemination plan of the GPT:

Per Section 3.5.3. Final Report in the Ghana FDA's Guidelines for Conducting Clinical Trials in Ghana, publication of the GPT results in a scientific journal or other medium for the purpose of disseminating the information obtained to stakeholders may be encouraged only after 30 days of acknowledgement of receipt of the Final Report (1 soft copy, 1 hard copy) by the Ghana FDA. After these 30 days, the following shall take effect:

1. According to **Grand Challenges Canada's** (GPT funder) Open Access Policy, we must *"make available to the public through open access channels the results of the research emerging from the Project, or any reports or other publications regarding the Project funded by this grant (collectively, the "Materials"), and anticipates that the Materials will be published in a treatise, thesis, trade publication or in any other format that is available for the interested public as soon as practical, consistent with the need to first secure intellectual property rights in a manner that maximizes the benefits to developing world interests. Specifically, the Grantee is expected to use good faith efforts and work in a collaborative fashion with its subcontractors and funders associated with the Project to facilitate broad dissemination and accessibility of the Materials in the developing world."* Therefore, we intend to make our results freely available on the Canadian **International Development Research Centre's** Open Access Digital Library and on our websites (www.girhl.org, www.icchange.ca).
2. For any papers accepted and published in peer-reviewed journals, we shall post a Word version of our peer-reviewed, accepted article on our organizational websites (www.girhl.org, www.icchange.ca) immediately after publication in print or online. The Word document will indicate the article's citation and a link to the published article on journal website.

In addition to the above dissemination plan, we will freely share our results and the Word version of our peer-reviewed, accepted article with the Korle Bu Teaching Hospital. If the hospital wishes, they may post the documents on the hospital website. We also intend to present our results at various conferences in the fields of sleep medicine, obstetrics, and global health. The Korle Bu Teaching Hospital will be acknowledged in all publications and presentations.

9 Ethical Issues

